### Inclusion criteria

- Diagnosis by ROME III/IV criteria.
- Willing to participate and informed consent is obtained.

### Exclusion criteria

- Presence of alarm symptoms such as severe organic GI diseases, unexplained iron deficiency anaemia, unintentional weight loss, palpable abdominal mass.
- No active substance intake.

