Melatonin is a hormone made by the pineal gland; its biosynthesis is initiated by the uptake of the essential amino acid tryptophan and is an important inducer of sleep. Abnormality in melatonin has been shown in several studies on patients of IBS and functional constipation. A few studies also reported improvement in sleep and GI function after administration of melatonin. However, these studies had limitations due to small sample size, lack of randomization and inclusion of patients without sleep disorder. Moreover, there is no study from India on this issue (5,6,7).

Accordingly, we wish to undertake a study with the following aims:

- (i) Quality of sleep among patients with IBS and healthy controls.
- (ii) Levels of 6-Hydroxymelatonin sulphate (metabolite of melatonin) both in patients with IBS and healthy controls.
- (iii) Relationship between the IBS symptom severity (IBS-SSS), Health-Related Quality of Life (HRQL) and sleep disorder and melatonin deficiency,
- (iv) Relationship between gut dysbiosis and the above parameters
- (v) Effect of melatonin administration on IBS symptoms, HRQL and sleep.

Since sleep disturbance may be an important issue in IBS, the patients with IBS will be treated both with melatonin and standard treatment. Parameters like IBS-SSS, HRQL (8), Hospital Anxiety and Depression Scale (HADS) score (9), Pittsburgh Sleep Quality Index (PSQI) (10) will be studied in patients with IBS and healthy controls and these parameters would be repeated after 1 and 3 months follow-up in patients only. Urinary 6-Hydroxymelatonin sulphate will be studied in patients and controls before treatment with melatonin and it will be repeated after one month among patients with IBS only. Sleep study will be performed by PSQI questionnaire and also by polysomnography depending on the availability of the instrument. Study will analyse the effect of melatonin in GI and sleep disorder functions. Data will be analyzed using appropriate statistical techniques. P-values lesser than 0.05 will be considered significant.

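### The substance-intake exclusion criterion has the wrong polarity: as written it excludes people who take nothing and does not exclude active users

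*Protocol*

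**What the plan says.** In the Study protocol part of the document, the list headed "Exclusion criteria" has two items. The first is "Presence of alarm symptoms such as severe organic GI diseases, unexplained iron deficiency anaemia, unintentional weight loss, palpable abdominal mass". The second is "No active substance intake".

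The list before it, Inclusion criteria, also has two items: "Diagnosis by ROME III/IV criteria" and "Willing to participate and informed consent is obtained". Neither concerns substance use.

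The Brief proposal summary gives the study two populations. Its first aim is "Quality of sleep among patients with IBS and healthy controls", and its second compares a urinary melatonin metabolite in the same two groups. The Sample size section plans 97 cases and 97 controls, with the 97 patients then randomised to melatonin or placebo.

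**The concern.** An exclusion list works by removal: a person for whom an item is true does not enter. An item that begins with a negation therefore removes the people who lack the condition. Taken at its word, this one bars every person who takes no substances and does nothing to bar an active user.

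The line is operative eligibility text. It is not background or a superseded version, and it makes up half of the exclusion list. If it is followed exactly, the wrong population is enrolled. If staff follow the evident intent instead, which is far more likely, every enrolled non-user is formally a breach of the written criteria, and the screening record contradicts the protocol.

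The subject of the rule is not incidental. The study measures sleep quality in patients and in healthy controls, and substance use can plausibly affect sleep. The patient-control comparison is not randomised, so who may enter each group has to be clear.

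**Working it through.** No arithmetic applies. The check is a reading of the criterion under its heading, against its neighbour, and against the rest of the document.

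**Step 1: how the list is framed.** The first exclusion item names something whose presence disqualifies (alarm symptoms). This confirms the ordinary convention: item true, person out.

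**Step 2: the same convention applied to the second item.**

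| Person screened | Is the item true? | Result under the written rule |
|---|---|---|
| No active substance intake | Yes | Excluded |
| Active substance intake | No | Not excluded by this item |

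The two items in the list therefore run in opposite directions. The first keeps out people who have the named problem. The second keeps out people who do not.

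**Step 3: does another rule override it?** The inclusion criteria cover the Rome diagnosis and willingness with consent. Neither would stop an active user from entering or restore a non-user.

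**Step 4: is it restated or corrected elsewhere?** The Brief proposal summary, the Sample size section, the project submission form and the ethics committee's list of suggestions contain no second statement of the criterion. The ethics committee's suggestions do not raise it.

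**Step 5: to whom does it apply?** The Rome criterion cannot apply to healthy controls, so the inclusion list as written is for patients. No separate criteria for controls appear in the text available. The document therefore does not settle whether the substance rule, in either direction, covers the controls.

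**Step 6: does it reach any figure?** The sample sizes rest on sleep-disorder frequencies of 40% in cases and 22% in controls, and on improvement rates of 88% and 47%. None of these uses the substance criterion, so all stand unaffected.

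**The case against.** The strongest reply is that this is a slip of wording that nobody will act on. The natural reading is that the second bullet states a condition for entry and landed under the wrong heading. The study is run at a single centre, so no remote site has to interpret the line unaided. A team applying the literal rule would be turning away non-users, healthy controls among them, and would notice at once. All of this stands. It limits the practical harm, but it does not make the written rule correct.

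A reader might go further in four directions, and the documents support none of them.

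- **That the trial intends, or is likely, to enrol only substance users.** Nothing suggests this. The framing of the neighbouring item points to an error of placement.
- **That the resulting bias in the comparison of cases and controls can be sized.** That would need the frequency of sleep disorder in users and in non-users, and the imbalance in use between the groups. The protocol gives none of these. Its 40% and 22% are averages for cases and controls, not split by substance use, so 22% cannot serve as a non-user rate. Nor does the wording error imply that the rule would be applied unevenly.
- **That the error strikes the trial's main endpoints.** The protocol lists symptom severity, quality of life, anxiety and depression, sleep quality and the melatonin metabolite without ranking them. The interventional sample size rests on improvement.
- **That failing to name the substances is itself an error.** It is missing detail, and it could sit in the case report form, which is not shown.

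**Conclusion.** The criterion is wrong as written. One of the two exclusion criteria has reversed polarity, and nothing in the available text corrects it. The conclusion rests only on the ordinary meaning of an exclusion list, which the other item in the list confirms. That the reverse was intended is an inference, though a very safe one.

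The finding is narrow. It is a probable drafting slip with an easily guessed intent, and it has no effect on the sample sizes or on any stated figure. It merits correction because eligibility is settled by the protocol's text, and this text cannot be followed without enrolling the wrong people. No numerical bias is claimed.

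**What to change.** Reconcile the wording with the heading in one of two equivalent ways: restate the exclusion positively, as active substance intake, or move "No active substance intake" unchanged to the inclusion list. In the same edit, state whether the criterion also applies to the healthy controls. If the case report form or a screening checklist repeats the line, correct it there too.

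The cost is a one-line protocol correction. Sample size and study procedures do not change.

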### Fund Requirements:

Detailed year wise breakup under the heading of staff, Equipment, Contingencies etc. (List of the items/ compounds may be given)

Amount of grant proposed: (in Rs.)

		Ist year	IInd year	Total
Staff	Junior Research Assistant	2,40,000	2,40,000	4,80,000
	(JRA)			
Contir	l ngencies	5,50,000	2,70,000	5,32,000
Equip	ments	Nil	Nil	Nil
Grand	total	7,90,000	5,10,000	13,00,000

## Contingencies:

DNA extraction kits, Oligonucleotide primers, SYBR® Green master mix, Melatonin-Sulfate Urine ELISA kit, other lab reagents and glassware, ladder, Agarose, Taq polymerase, dNTPs, PCR tubes, Microtips, pipettes, gut microbiota next-generation sequencing.

#### AN7-V3/SGSOP 03/V3

### AN13-V1/SGSOP 03/V1

Checklist of Documents (6 copies and a CD of all documents listed below)
(Non Interventional trial require documents listed in Item no. 1 to 13)

Please give page no. to all documents (start from 1, 2, 3..............40 and so on.)

\*Please provide version no. and date of each document (for drug/device trial)

Protocol Title: Frequency of sleep abnormalities in patients with irritable bowel syndrome and its relationship with symptom severity, quality of life and effect of pharmacological intervention to improve sleep on these parameters

Principal Investigator: [name] [name], Professor, Gastroenterology, SGPGI

Type of document: Independent project

Item No.	Mandatory Documents (*with version and date)	Yes	No	NA	
1.	Document Receipt Form (to be submitted in duplicate, AN14-V1/SGSOP 03/V1)	~	,		Page No.
2.	Project Submission Form (AN1-V1/SGSOP 03/V1)	·/			1-6
3.	Study Protocol (Review of literature, aim, methodology, inclusion, exclusion criteria)				9-17
4.	Case Report Form (form to capture data)				
5.	Consent of Head of the PI's Department (AN2-V1/SGSOP 03/V1)				68
6.	Research committee/department committee /doctoral committee/scientific committee approval (AN3-V1/SGSOP 03/V1)		\$		19
7.	Undertaking by the PI (AN4-V1/SGSOP 03/V1)				20 - 21
8.	Conflict of Interest Statement by PI (AN5-V1/SGSOP 03/V1)				22
9.	CV of new or investigator outside SGPGI or of the student (AN6-V1/SGSOP 03/V1)			MA	
10.	Participant Information document (PID) & consent forms CF) in English and Hindi (and if required in any other language) (AN 7to 10 -V1/SGSOP 03/V1) * Include guardian and parents				21-37
11.	Child Information Document and assent form in English and Hindi (and if required in any other			MA	

	language) (AN11-12-15V1/SGSOP 03/V1)			
12.	Ethics Committee clearance of other centers (in case of collaborative project)	, i	NA	
13.	Clinical Trials Registry- India (CTRI) is a pre- requisite for clinical trials. In other case this must be done after approval by IEC	-	,	will be applied a gleice
14.	Investigator Brochure		HA	
15.	Advertisement/Information brochure		MA	
16.	Insurance policy and certificate		MA	
	DCGI approval letter/DCGI submission letter		MA	
18.	NOC from DCGI /ICMR/DBT		MA	
19.	Director General of Foreign Trade (DGFT) approval in case study samples are to be sent abroad for analysis		HA	
20.	Genetic Engineering Advisory Committee (GEAC) approval in case study involves use of gene therapy/recombinant DNA		ŊA	
21.	Bhabha Atomic Research Centre (BARC) approval in case study involves use of radioisotopes/ionizing radiations		μA	
22.	Stem cell (NAC-SCRT registration and approval)		MA	
23.	DCGI marketing/manufacturing license for herbal formulations/nutraceutics		NA	
24.	Clinical Trial Agreement (CTA)/Memorandum of Understanding (MOU)		МА	
25.	Material Transfer Agreement (MTA)- Health Ministry Screening Committee (HMSC) approval in case the study involves collaboration with any foreign laboratory/clinic/institution		нА	
26.	IEC processing fee (applicable for sponsored trials)		MA	
27.	Any other documents		-	

## Checklist to assess the projects before they are submitted to IEC review

Item No.	Mandatory Documents (*with version and date)	Yes	No	NA	Page No.
1.	Document Receipt Form (to be submitted in duplicate, AN14-V1/SGSOP 03/V1)				•
2.	Project Submission Form (AN1-V1/SGSOP 03/V1)				1-6
3.	Study Protocol (Review of literature, aim, methodology, inclusion, exclusion criteria)	~			9-17
4.	Case Report Form (form to capture data)				
5.	Consent of Head of the PI's Department (AN2-V1/SGSOP 03/V1)	~			18
6.	Research committee/department committee/doctoral committee/scientific committee approval (AN3-V1/SGSOP 03/V1)	~			19
7.	Undertaking by the PI (AN4-V1/SGSOP 03/V1)	~			20-21
8.	Conflict of Interest Statement by PI (AN5-V1/SGSOP 03/V1)	~			22
9.	CV of new or investigator outside SGPGI or of the student (AN6-V1/SGSOP 03/V1)			NA	
10.	Participant Information document (PID) & consent forms CF) in English and Hindi (and if required in any other language) (AN 7to 10 -V1/SGSOP 03/V1) * Include guardian and parents				24-34
11.	Child Information Document and assent form in English and Hindi (and if required in any other language) (AN11-12-15V1/SGSOP 03/V1)			NA	
12.	Ethics Committee clearance of other centers (in case of collaborative project)			NA	
1 3 .	Clinical Trials Registry- India (CTRI) is a pre-requisite				will be ap

	for clinical trials. In other case this must be done after	
	approval by IEC	
14.	Investigator Brochure	NA
15.	Advertisement/Information brochure	NA
16.	Insurance policy and certificate	NA
17.	DCGI approval letter / DCGI submission letter	MA
18.	NOC from DCGI /ICMR/DBT	NA
19.	Director General of Foreign Trade (DGFT) approval in case study samples are to be sent abroad for analysis	NA
20.	Genetic Engineering Advisory Committee (GEAC) approval in case study involves use of gene therapy/recombinant DNA	NA
21.	Bhabha Atomic Research Centre (BARC) approval in case study involves use of radioisotopes/ ionizing radiations	NA
22.	Stem cell (NAC-SCRT registration and approval)	NA
23.	DCGI marketing/manufacturing license for herbal formulations/ nutraceutics	NA
24.	Clinical Trial Agreement (CTA)/Memorandum of Understanding (MOU)	NA
25.	Material Transfer Agreement (MTA)- Health Ministry Screening Committee (HMSC) approval in case the study involves collaboration with any foreign laboratory/clinic/institution	NA
26.	IEC processing fee (applicable for sponsored trials)	
27.	Any other documents	طدي

